In Summary, some of the immediate potential benefits of non-invasive VNS could include: control of headache intensity, decreasing the side effects of narcotic and steroid use, prevent DCI and strokes due to SAH, prevent seizures, decrease the SIRS response by regulating the sympathetic nervous system and regulating α 7nAChR, and decrease ICU and hospital length of stay due to decrease usage of opiates leading to loss of neurologic examination and leading to unnecessary testing.

Some of the long-range potential benefits might include decreased readmission rates from headache due to SAH, decrease outpatient usage of opiates, and prevent opiate dependency and improving recovery through enhancing neuroplasticity.

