3 OBJECTIVES AND ENDPOINTS

The primary outcome measurement for effectiveness is:

-The difference between the active and sham treatment groups in mean daily morphine equivalence dosage during study

Secondary endpoints include descriptive comparisons between the active and sham treatment groups in:

- The difference in mean daily headache intensity during the study

The difference between total overall morphine equivalence dosages per subject during study
 Opiate related adverse events (such as urinary retention, constipation, sedation, nausea, vomiting and pruritis)

- The difference in cytokines levels and brain permeability markers in the blood and/or CSF before and after stimulation and between the sham and active device group

- Effects of VNS on brain permeability measured through CT perfusion studies

-The difference in modified rankin scale at hospital discharge and during outpatient follow up. This will be collected retrospectively from the follow up outpatient visit.

Exploratory analyses will include descriptive comparisons of the rates of stroke, vasospasm, DCI, seizure, central fever and severity of vasospasm between the active and sham treatment groups.

OBJECTIVES	ENDPOINTS
Primary Objective:	

Incidence of device related serious adverse events.	Proportion of patients with device related adverse events
The difference between the active and sham treatment groups in mean daily morphine equivalence dosage during study	Morphine equivalence dosage will be calculated per day.
Secondary Objectives	
The difference between the active and sham treatment groups in the mean daily headache intensity during the study	Headache intensity will be measured throughout the day and a mean daily headache intensity will be calculated.
The difference between total overall morphine equivalence dosage between the active and sham group per subject during study	Total morphine equivalence dosage for the duration of the study will be calculated.
Incidence of opiate related adverse events (such as urinary retention, constipation, sedation, respiratory depression, nausea, vomiting and pruritis)	Number of patients with of urinary retention, constipation, sedation, nausea, respiratory depression, vomiting and pruritis.

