The difference in cytokines levels and blood brain permeability markers in the blood and/or CSF before and after stimulation and between the sham and active group	When possible, cytokines levels and permeability markers will be measure in the blood and/or serum just before the first vagus nerve stimulation and approximately 24 hours later, after the 11:30 AM stimulation session. If possible, this will be repeated on day 5 and 7 post-ictus as it is the period of cerebral vasospasm

	Immunologic investigations include but not limited to, measurement of inflammatory protein levels, RNA		
	sequencing of leukocyte and stimulation assays.		
Evaluate the effects of VNS on	The integrity of the blood brain barrier will be evaluated		
blood brain barrier integrity	through CT perfusion if performed as standard of care.		
Exploratory objectives			
Comparisons of the rates of stroke, vasospasm, DCI, seizure, and central fever between the active and sham treatment groups	Neuroimaging upon admission and at discharge will be compared and evidence of new strokes will be noted. The presence of DCI (change in neurologic examination thought to be due to vasospasm) will be evaluated.		
	Transcranial doppler velocities will be compared between the active and sham groups		
	The number of days with central fever will be compared between the active and sham groups		
	Incidence of seizures will be compared between the active and sham groups		
Effect of nVNS on severity of cerebral vasospasm during DSA	Rate of change in the severity of cerebral vasospasm will be noted before and during or after nVNS		

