8 STUDY ASSESSMENTS AND PROCEDURES

8.1 EFFICACY ASSESSMENTS

Per standard of care, patients presenting with signs of SAH like acute severe headache, will get a diagnostic head CT which confirms blood in the subarachnoid space. If patients have symptomatic hydrocephalus (altered mental status with CT head consistent with hydrocephalus) an external ventricular drain will be placed. Most patients will get either a CT angiogram or a conventional angiogram to rule out a vascular malformation, especially if there is no history of trauma. If an aneurysm is detected, the standard of care is to treat it as soon as possible. Usually, an aneurysm iseither coiled or clipped (craniectomy or craniotomy). Every patient admitted with subarachnoid hemorrhage will get graded accordingly to their headache intensity, level of consciousness and neurologic deficits with the Hunt Hess grade (table 2). Their CT scans also get graded (modified fisher scale mFS) according to the thickness and location of blood (table 3). All subarachnoid hemorrhage (unless there is minimal amount of blood and no vascular malformation) are admitted to the Neurosurgical care unit (NSCU). Detailed physical examination, including the NIHSS, history, including medication history, past medical, surgical history, and social history are recorded in the medical records. North Shore University hospital NSCU is the referral center for most of the hospitals in Northwell health care system. Most aneurysmal SAH patients get transferred to our unit. Per standard of care, all women of child bearing age, admitted to the NSCU get a urine or blood pregnancy test, patients suspected of abusing drugs get urine toxicology. Once in the NSCU, patients get vital signs and neurologic assessment every hour, and pain assessment every 4 hours and as needed. The length of stay in the intensive care unit depends on the amount of blood on the head scan (mFS). Patients with higher mFS are more prone to get delayed cerebral ischemia. As a result, per standard of care, patients with SAH get almost daily transcranial dopplers to monitor for cerebral vasospasm, frequent head scans, occasionally brain perfusion studies and MRI of the brain. Patients are monitored for central fever (vital signs, blood cultures), cerebral salt wasting with frequent BMP and urine output measurements, seizures with PRN electroencephalograms (EEG). Once out of the critical care period, (vasospasm usually starts at day 3 post bleeding and peaks at day 10), patients get transferred to a regular neurosurgical floor before being discharged home or to rehabilitation. On average patients stay in the NSCU between 2-21 days. All patients admitted to the NSCU with SAH will be screened and evaluated for the inclusion and exclusion criteria after obtaining an informed consent.

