- Constipation evaluated by the need for enema, suppository, lactulose or magnesium oxide administered
- Blood tests, CSF studies
- EEG results
- Neurologic examination including Glasgow coma score, and NIHSS
- Delirium score

When Transcranial dopplers are being done as per standard of care, we will assess the changes in transcranial velocities around the time of the stimulation of the Vagus nerve.

When possible, we will draw blood or in case there is an EVD we will also collect CSF for biomarkers. Not more than 5 ml of blood will be drawn before the 11:30 am stimulation session of the Vagus nerve. This will be repeated approximately 24 hours later, at 11:30 am post VNS stimulation session. This might be repeated on days 5 and 7 post-ictus In case there is an EVD, 2 cc of CSF from the drain and 20 cc of CSF that is otherwise discarded will be drawn before the 11:30 am stimulation session of the Vagus nerve. Another 2 cc of CSF from the drain and 20 cc of CSF that is otherwise discarded will be drawn before the 11:30 am stimulation session of the Vagus nerve. Another 2 cc of CSF from the drain and 20 cc of CSF that is otherwise discarded will be drawn approximately 24 hours later, at around 11:30 am post VNS stimulation session. This might be repeated on days 5 and 7 post-ictus.

The CSF will not be taken from the proximal port of the EDV unless it is being tested for CSF cell count or cultures as per standard of care. This is in order not to increase the risk of infection.

Deidentified blood and CSF will be sent to [name], academic chief in the department of stroke and vascular neurology, Yale, [name].

IF CT perfusion is being performed per standard of care between days 3-10, blood brain permeability will be evaluated and results will be compared between the sham group and the active device group.

During the period of the study after the patients are discharged from the ICU to the Neurosurgical floor, we will evaluate their daily headache intensity and morphine equivalence dosage, in addition to their TCD results, Neuroimaging and EEG results, neurologic examination and vital signs.

Table 2: Hunt-Hess Score in aneurysmal SAH: (26, 27)

- 1. Asymptomatic, mild headache, slight nuchal rigidity
- 2. Moderate to severe headache, nuchal rigidity, no neurologic deficit other than cranial nerve palsy
- 3. Drowsiness, confusion, mild focal neurologic deficit
- 4. Stupor, moderate-severe hemiparesis
- 5. Coma, decerebrate posturing

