Title: Safety and efficacy of non-invasive Vagus Nerve Stimulation (nVNS) in the treatment of headache in Subarachnoid Hemorrhage (SAH)

MAY, 1, 2022

NCT04126408

Overview of study design

This is a single site, randomized, sham-controlled, double-blind study assessing the feasibility, safety, tolerability, and efficacy of non-invasive VNS (nVNS) in the treatment of headache in subarachnoid hemorrhage (SAH).

We hypothesize that two two-minute noninvasive stimulations of the cervical branch of the Vagus nerve, every 5 hours, is efficacious in safely reducing headache intensity and frequency in patients with headache due to SAH, during the patient's intensive care unit (ICU) stay.

After screening and obtaining informed consent, eligible patients diagnosed with SAH on head scans, admitted to the Neurosurgical Intensive Care Unit (NSCU) at Northshore University Hospital will be randomized to either the treatment (stimulation of the cervical branch of the Vagus nerve) or sham (inactive stimulation) group.

Pain intensity will be evaluated every 4 hours. Non-invasive stimulation will be performed every 5 hours.

The treatment arms are the following:

Group 1: Control (patients will receive treatment using an inactive VNS device)

Group 2: Treatment (patients will receive treatment using an active VNS device)

The patients are randomized with equal probability to one of the treatment arms. In total, approximately 40 patients will be recruited

Primary objective

The primary objective of this study is to evaluate the effectiveness of VNS compared to sham device as measured by the mean daily morphine equivalence dosage during the study

Secondary Objectives

The secondary objectives of the study are to compare VNS to sham treatment with respect to effects on the following:

- total overall morphine equivalence dosage
- mean daily headache intensity during the study
- cytokines levels
- blood brain permeability markers in the blood and/or CSF before and after stimulation
- blood brain barrier integrity

Exploratory objectives:

- stroke, vasospasm, DCI, seizure, and central fever
 - The presence of DCI,
 - Transcranial doppler velocity,
 - The number of days with central fever,
 - Incidence of seizures
- severity of cerebral vasospasm during DSA

Safety objectives:

- Opiate related adverse events (such as urinary retention, constipation, sedation, nausea, vomiting and pruritis)
- Occurrence of Adverse Events (AEs)/Serious Adverse Events (SAEs)
- Vital Signs

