- Modified ITT (mITT): A modified Intent-to-treat (mITT) population inclusive of all ITT subjects who are treated at least 7 days with at least 3 stimulations of the study device.
- The Per Protocol Set (PPS): Patients who are compliant with the treatment regimen for the duration of the study will be analyzed.
- The safety set will consist of all randomized patients who received at least one stimulation.

The mITT is considered as the primary analysis dataset and will be used for all primary and secondary efficacy analyses. The primary efficacy analyses will be repeated using the PP set. Any discrepancy between the results from the mITT and the PP will be analyzed and discussed.

The secondary variables will be analyzed based on mITT only.

Baseline data and safety analysis will be based on the safety set.

Patient characteristics

In general, data will be summarized by means of summary statistics. Continuous data will be presented with the number of observations, mean value, standard deviation, minimum, median and maximum value. The mean, standard deviation and median will be given with one decimal more than the original values. When applicable, values at each visit, as well as changes from baseline, will be summarized.

Categorical data will be presented as counts and percentages. The data will be presented for each treatment group by visit.

Patient demographics and vital signs will be summarized for all randomized patients. For each of the variables, the treatment group difference will be examined using T-test for continuous variables, and Fisher's exact test for categorical variables.

Efficacy Analysis

The primary analysis of the primary efficacy variable will be based on the mITT population set.

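### Blood-brain-barrier integrity is tested between arms only in patients who happen to have a clinical CT perfusion scan, a comparison that randomisation does not protect

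*Protocol*

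**What the plan says.** Protocol section 3 lists "Effects of VNS on brain permeability measured through CT perfusion studies" among the secondary endpoints, and its objectives table says barrier integrity will be assessed "through CT perfusion if performed as standard of care". Section 8.1 repeats the condition and adds a time window: "IF CT perfusion is being performed per standard of care between days 3-10, blood brain permeability will be evaluated and results will be compared" between sham and active. The origin of the day count is not given. No CT perfusion is required by the study. The schedule of activities includes CTA/CTP under imaging, but section 10.1.7 says the imaging reports collected are those from standard-of-care studies. Section 8.1 describes routine care as including "occasionally brain perfusion studies and MRI of the brain".

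The SAP lists "blood brain barrier integrity" as a secondary efficacy variable, separate from the blood and CSF permeability markers. For secondary and exploratory variables alike, it compares the randomised groups by t-test or Fisher's exact test at each visit, with all tests two-sided at 0.05. On the analysis set it says "The secondary variables will be analyzed based on mITT only". Protocol section 3, by contrast, introduces the list with "Secondary endpoints include descriptive comparisons between the active and sham treatment groups in".

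Neither document plans to report the scanning rate by arm, compare scanned with unscanned patients, or label the result a subset analysis.

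**The concern.** Whether a patient has a CT perfusion value is generally settled after randomisation, by a clinical decision. If treatment influences that decision, the scanned patients in the two arms differ in ways other than treatment, and a t-test or Fisher's test attributes that difference to the device.

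The protocol supplies two routes by which treatment could act. Section 2.3.2 lists among the potential benefits that nVNS could "prevent DCI and strokes due to SAH", and section 8.1 presents the imaging as part of surveillance in patients prone to DCI. Section 2.1 says opiates disturb the neurological examination and prompt unnecessary tests, and opiate dose is the primary efficacy endpoint. Blinding closes neither route, because both run through the patient's clinical course.

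A true benefit could therefore be diluted, or a spurious difference could appear. The pilot is meant to inform a larger trial, so a misleading result here could affect the choice of endpoints there.

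**Working it through.** **Inputs from the documents.** About 40 patients randomised 1:1, so at most 20 per arm (SAP, overview). Two-sided 0.05 (SAP, general approach). Scanning is occasional, with no percentage given (protocol 8.1). The documents give no SD, effect size or scanning share for this variable and no justification of the sample size, so there is no plan figure to reproduce. Everything below is illustration on stated assumptions.

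**1. Dilution of a real effect.** Assume that severity is N(0,1) on sham and N(-0.5,1) on active, that permeability is also lowered by 0.5 SD on active, that the two correlate at rho, and that a scan is done when severity exceeds a threshold c. Let λ(c) = φ(c)/(1 − Φ(c)). Mean permeability among the scanned is rho·λ(c) on sham and −0.5 + rho·λ(c + 0.5) on active. The fraction of the effect lost is

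rho × [λ(c + 0.5) − λ(c)] / 0.5.

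| c | Scanned, sham v active | Patients of 20 | λ(c + 0.5) − λ(c) | Loss, rho 0.3 | rho 0.5 | rho 0.7 | rho 1 |
|---|---|---|---|---|---|---|---|
| 0 | 50% v 31% | 10 v 6 | 1.141 − 0.798 = 0.343 | 21% | 34% | 48% | 69% |
| 0.5 | 31% v 16% | 6 v 3 | 1.525 − 1.141 = 0.384 | 23% | 38% | 54% | 77% |
| 1.0 | 16% v 7% | 3 v 1 | 1.939 − 1.525 = 0.414 | 25% | 41% | 58% | 83% |

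At rho = 1 the differences left among the scanned are 0.157, 0.116 and 0.086 SD.

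**2. A spurious difference when there is no effect on permeability.** Assume that permeability correlates at rho with baseline severity, that a scan is done when severity plus independent noise of equal variance exceeds a threshold, and that treatment changes only the scanning rate. By simulation:

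- Equal scanning rates: bias is 0 within simulation error, and type I error is 4.9% at 50% v 50% with rho 0.5.
- Active scanned 15 points less often (sham rates 30-75%, rho 0.3-0.7): bias against active is 0.05 to 0.20 SD.
- Type I error: 5.3% at 50% v 35% (rho 0.5), 6.1% at 30% v 15% (rho 0.7), 7.1% at 50% v 25% (rho 0.7).

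**3. Precision.** With n scanned per arm, the detectable difference d at 80% power comes from the noncentral t distribution with 2n − 2 degrees of freedom and noncentrality d√(n/2). Power for 0.8 SD is approximately Φ(0.8√(n/2) − 1.96).

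| Scanned per arm | Detectable difference | Power for 0.8 SD |
|---|---|---|
| 20 | 0.91 SD | 72% |
| 15 | 1.06 SD | 59% |
| 10 | 1.32 SD | 43% |
| 5 | 2.02 SD | 24% |

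The mITT restriction can only lower these counts.

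**4. Timing.** Section 4.1 allows enrolment up to day 5 after aneurysm treatment, while the scan window opens at day 3 from an unstated origin. A scan could therefore precede randomisation or first stimulation, and no rule excludes it.

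**The case against.** The strongest reply is that the path from treatment to scanning is inferred. Section 8.1 ties surveillance to the modified Fisher grade, which is read from CT and recorded at screening. Selection on a baseline grade alone would leave the scanned groups comparable in expectation. Nothing says that CT perfusion is triggered by deterioration under treatment. The trial is sham-controlled in one unit with blinded patients and assessors, and no difference in ordering practice between arms is described, although the ordering clinician is not named separately in the blinding text. The DCI benefit is stated only as a possibility, and DCI is an exploratory outcome.

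Most of this stands, and it limits the point. A reader might infer that the scanned subsets are non-comparable. The documents do not support that; they support only that randomisation does not guarantee comparability. A reader might also take 69-83% as the expected loss, but that range requires severity and permeability to be the same variable.

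Nor does the argument carry over unchanged to vasospasm severity at DSA. Section 3 defines that endpoint as a change around a stimulation within the same patient, and it is already exploratory. Only a between-arm comparison among patients sent for DSA shares the problem.

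The protocol's descriptive wording and its statement that there are no statistical hypotheses soften the consequence. They do not answer the point, because the SAP tests the variable anyway.

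**Conclusion.** The point holds, as a minor one. A variable observed only when clinicians order a scan is given a between-arm test in the SAP, against the protocol's descriptive label and without any account of who was scanned. The comparison is unbiased if treatment leaves scanning unchanged. If the protocol's hypotheses on DCI or opiates are right, treatment would change it.

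Under the assumed 0.5 SD shift and threshold ordering, the loss runs from about a fifth to somewhat over a half of the effect for correlations of 0.3 to 0.7. With no effect on permeability, the assumed differences in scanning raise type I error only to 5.3-7.1%. Imprecision is probably the larger problem: at 5 scanned per arm, only a difference of about 2 SD is detectable with 80% power. The real scanning rates, the correlation and the ordering triggers are unknown from the documents.

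**What to change.** In the SAP, remove the between-arm test for barrier integrity by CT perfusion and present the variable descriptively as exploratory; align the listing in protocol section 3. Relabelling alone is not enough, because the SAP applies the same tests to exploratory variables. In addition:

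- Report the number and share scanned by arm, with indication, scan day and timing relative to first stimulation.
- Tabulate baseline modified Fisher and Hunt-Hess grades for scanned and unscanned patients by arm.
- Define the origin of the day 3-10 window and count only scans after first stimulation.
- State that no treatment inference is drawn from the scanned subset.
- For vasospasm severity at DSA, report the number imaged by arm and treat any between-arm comparison as descriptive.

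The cost is wording and a few added tables from data already collected or in the medical record, with no extra scans or patients. The downside is one fewer tested secondary endpoint. The blood and CSF permeability markers are a separate variable and are not affected.

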8.2 SAFETY AND OTHER ASSESSMENTS

nVNS has been proven to be safe. However, the risks of VNS in SAH population are not known. In order to minimize the risks, if an aneurysm has been identified to be the cause of the SAH, patients will only be enrolled if the aneurysm has been completely treated. This information will be pulled from the medical record. Past medical and surgical history, respiratory and hemodynamic state will be pulled from the medical record. Vital signs and neurologic examinations are usually performed every 1 to 4 hours depending on the acuity of each case, and pain assessment evaluated every 4 hours and as needed. In the NSCU, patients are on continuous ECG analyzes via telemetry. Stimulation will only be given if HR >60 and the SBP>100 mmHg, MAP> 60 mmHg and oxygen saturation is >90% for safety concerns. The presence of intolerable pain at the stimulation site, skin irritation, hoarseness, and change in the taste, shortness of breath, chest pain, nausea, and vomiting will be evaluated.

Safety outcomes:

- Rate of Symptomatic bradycardia defined as a drop in HR to less than 60 beats per minutes with symptoms, not due to nimodipine. The timing of nimodipine relative to the VNS will be recorded. All patients are on telemetry during the stimulation.
- Rate of drop in blood pressure, defined as a drop in blood pressure requiring fluid resuscitation or vasopressor support thought to be due to the device.
- Rate of side effects: presence of intolerable pain at the stimulation site, skin irritation, nasopharyngitis, hoarseness, dysgeusia, shortness of breath, chest pain, nausea and vomiting.

Figure

Days 1-3	Screening			
 Total n=40 Obtain informed consent Screen potential participants by inclusion and exclusion criteria Obtain history, document Randomize 				
Days 2-4 till discha from ICU	rge Baseline assessments/ Study Intervention			
 Obtain daily cumul Evaluate presence Evaluate seizures d Complete vital sign Questionaire for sign 	as before and after each stimulation and daily trend de effects from VNS post every stimulation scranial dopplers (TCD) comatic vasospaspm I fever			
Discharge from the hospital or day 10 post-ictus				

